7.2 Sample Size and Accrual

The study will enroll 17 eligible patients that are being treated at UNC Hospitals.

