1.3 Purpose and Rationale

This is a prospective study of the use of combined PET-MR [1-7] for prediction of tumor subtype composition in ccRCC. Additional data analysis using the prior study from UNC suggests a strong correlation between the fraction of the tumor exhibiting moderate to high FDG uptake and the number of cores found to be ccB type. These results guide the hypothesis of this study: the metabolically-active tumor volume fraction derived from simultaneous PET-MRI imaging of clear-cell renal cell carcinomas is correlated with the fraction of tumor cores classified as ccB subtype from transcriptome analysis. If so, in the future, application of PET-MRI may offer prognostic information and opportunities for risk stratification.

We propose that the results of a single PET-MRI study prior to surgery will predict ccA/ccB content of the tumor. Patients will have clinically-suspected ccRCC based on prior imaging, with tumor size $\geq 4\text{cm}$. Subjects must have a planned nephrectomy schedule that will allow PET-MRI imaging within 4 weeks prior to surgery. Once patient identification occurs, the patient will be assessed for the study via the inclusion and exclusion criteria. Among other criteria, patients must have no contraindications against 18F-FDG PET nor MRI with gadolinium contrast. After recruitment by the study coordinator and informed consent, the patient will be admitted to the study and scheduled for imaging.

Patients in our study will receive their PET/MRI scan on the Biograph mMR combined PET-MRI scanner at the Biomedical Research Imaging Center. The PET-MRI scans will be evaluated retrospectively and will not be used in the determination of treatment.

Quantitative measures from PET and MRI will be computed: Quantitative measures from PET will be computed, including tumor maximum SUV, tumor mean SUV, and fraction of tumor volume over threshold SUV 2.0 (FTVOT2), as well as Metabolic Tumor Volume (MTV) and Total Lesion Glycolysis (TLG).

Quantitative measures from MRI will be computed including tumor volume, apparent diffusion coefficient, dynamic contrast enhancement, and tumor water content. All quantitative measures will be compiled into a complete image-based characterization of each tumor.

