3.1.1 Age \geq 18 years of age (no upper age limit)

3.1.2 Has voluntarily provided signed informed consent to participate and HIPAA authorization for release of personal health information.

3.1.3 Must have clinically-suspected ccRCC based on prior imaging with tumor size \geq 4 cm.

3.1.4 Planned to have standard of care nephrectomy with a schedule that can accommodate a MR-FDG-PET scan within 4 weeks prior to surgery.

3.1.5 Must be able to understand and comply with study procedures for the entire length of the study.

3.1.6 Must receive their nephrectomy at UNC Chapel Hill Hospitals.

3.1.7 If patient has a history of prior malignancy, including melanoma, patient must be cancer-free for three or more years. Non-melanoma skin cancers will be included even if not cancer-free for three years.

3.1.8 Women of childbearing potential must have a negative urine pregnancy test performed the day of and prior to PET/MRI imaging.

3.1.9 Willing to undergo finger-stick blood glucose tests.

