4.5 Duration of Study Intervention

The study intervention is complete once the patient receives their PET-MRI scan. The patient may be withdrawn from the study prior to this point if any of the following apply:

- Inter-current illness prevents completion of imaging studies
- Unacceptable adverse event(s) prevents completion of imaging studies
- Patient decides to withdraw from the study, **OR**
- General or specific changes in the patient's condition render the patient unacceptable for completion of study in the judgment of the investigator.

After PET-MRI, patients will undergo nephrectomy as planned and per standard of care and tumors will be sampled as above (up to 10 cores will be taken from each tumor post-surgery and classified as ccA or ccB subtype using transcriptome analysis).

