6.0 EXPECTED RISKS/UNANTICIPATED PROBLEMS

6.1 Assessment of Safety

In general, any patient enrolled on this protocol and who undergoes any portion of the PET-MRI study (including gadolinium administration) will be evaluable for adverse events.

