7.0 STATISTICAL CONSIDERATIONS

7.1 Study Design/Study Endpoints

The purpose of the study is to assess the utility of combined, simultaneous positron emission tomography (PET) and magnetic resonance imaging (MRI), collectively called PET-MR, in predicting the fraction of tumor cores expressing the ccB subtype. The overall design is to image patients with PET-MR prior to surgery and evaluate quantitative metrics from imaging, and to evaluate the correlation of imaging metrics with the results of post-surgery transcriptome analysis. The primary endpoint is to correlate the MRI-guided PET metric fractional tumor volume over threshold SUV > 2.0 (FTVOT2) with the fraction of tumor cores classified as ccB from transcriptome analysis.

Patients will have suspected ccRCC based on imaging with tumor size ≥ 4 cm and for whom surgical treatment is planned. Once patient identification occurs, the patient will be assessed for the study via the inclusion and exclusion criteria mentioned above. The patient will then be approached by a study coordinator and

the study protocol explained and all risks outlined. If the patient provides informed consent the patient will be enrolled. Demographic data such as patient age, gender, comorbidities, and previous treatments, etc. will be collected. Tumor characteristics will be collected. All data collected will be kept on a password protected, secured server, and all physical documentation will be stored in a locked cabinet. All data will be collected by the PI, co-investigators and study coordinators.

Patients will then be scheduled for a pre-surgery PET-MR within four weeks of planned surgery.

For all PET scans, patients will be instructed to fast, and blood glucose level will be measured prior to injection of FDG; if blood glucose exceeds 200 mg/dL after two finger-stick tests, the patient will be rescheduled for another day or excluded from the study. Patients will be injected with approximately 12 mCi 18F-FDG, and then imaged starting 60 minutes post-injection for ten minutes each at one or two bed positions focused on the primary tumor site. MRI sequences to be run will include conventional anatomic T1- and T2-weighted sequences, high-resolution T1 pre- and post-contrast DCE sequences, and the PET-MR attenuation-correction sequence.

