The PET-MRs will be evaluated retrospectively by study personnel as to the size of the lesion, the FDG activity as measured by tumor-maximum and tumor-mean standard uptake values (SUVs), additional PET metrics (metabolic tumor volume (MTV) and total lesion glycolysis (TLG)), the presence or absence of invasion to adjacent organs, and the presence or absence of metastatic or multifocal disease. PET images will be evaluated with aligned anatomical MRI for guidance as well as determination of the tumor margins for computation of tumor-mean SUV, and FTVOT2.

The pathological specimens will be evaluated by a UNC pathologist. Again, all data will be stored on a secured, password protected server. Up to ten samples will be taken from each tumor, spatially distributed, and stored according to lab manual. Non-ccRCC histologies will be excluded from further analysis. RNA will be extracted and each sample will be classified as ccA or ccB using the ClearCode34 Nanostring classifier as previously described using a 34-gene custom Nanostring probe (NanoString Technologies, Seattle, WA).[13] Each sample will then be categorized as ccB or ccA or equivocal. If both tumor types appear in the same sample, the classifier will choose the closest match; however, each result will be reviewed and samples that show clear elements of both types in expression patterns will be labeled as equivocal. The fraction of samples classified as clearly ccB will be used in further analysis.

To address the primary endpoint, FTVOT2 will be evaluated and recorded for each subject as will the fraction of samples classified as ccB.

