7.3 Data Analysis Plans

For the primary endpoint, each subject's FTVOT2 will be correlated with the primary outcome (fraction of core classified as ccB) and correlation estimated using the non-parametric Spearman correlation test.

Regarding the specific hypothesis testing of PET FTVOT2, with $N = 17$, we will have approximately 54% power to detect a correlation of $\rho = 0.5$ (and 74% power to detect $\rho = 0.6$), with a Type I error rate of 0.05 and utilizing the Spearman correlation test. This is considered a conservative estimate. Data from the prior study¹ shows a strong Spearman correlation ($\rho = .896$, $p = .006$) between the fraction of core samples classified as ccB and the PET tumor volume fraction over SUV 2.0 (FTVOT2).

¹ S. A. Brooks et al., "Alternate metabolic programs define regional variation of relevant biological features in renal cell carcinoma progression," *Clinical Cancer Research*, Jan 19, 2016. (PMID: 26787754)

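### If 17 is the number enrolled, as section 7.2 says, the 54%/74% power in section 7.3 is a zero-loss maximum; section 1.1 can be read as 17 confirmed ccRCC cases, so the sections need reconciling

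*Combined protocol and SAP*

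**What the plan says.** Section 7.2 is one sentence: "The study will enroll 17 eligible patients that are being treated at UNC Hospitals". Section 7.3 takes N = 17, a type I error rate of 0.05 and the Spearman test, and says "we will have approximately 54% power to detect a correlation of" 0.5, with 74% at 0.6. It calls this conservative and then cites a Spearman correlation of .896 from the pilot.

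Other sections fix what enrolment means and who can drop out afterwards:

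- **Timing of enrolment.** Section 7.1: "If the patient provides informed consent the patient will be enrolled". Section 1.3 gives the same order: "After recruitment by the study coordinator and informed consent, the patient will be admitted to the study and scheduled for imaging".
- **Entry standard.** Section 3.1.3: "Must have clinically-suspected ccRCC based on prior imaging with tumor size" of at least 4 cm. Histological confirmation is not required.
- **Loss before the scan.** Section 4.5: "The patient may be withdrawn from the study prior to this point if any of the following apply", the point being receipt of the PET-MRI.
- **Loss after surgery.** Section 7.1: "Non-ccRCC histologies will be excluded from further analysis".
- **Enrolled versus imaged.** Section 6.1 describes the patients evaluable for adverse events as "any patient enrolled on this protocol and who undergoes any portion of the PET-MRI study", so being enrolled and being scanned are separate conditions.

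Section 1.1 attaches the same number to a different group: it speaks of imaging 17 ccRCC subjects, and of studying the relationship between imaging and subtype in 17 such subjects.

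**The concern.** The same number serves as an accrual count in 7.2 and as an analysis count in 7.3, and the protocol itself provides for losses between the two. A patient withdrawn before the scan has no FTVOT2. A patient whose tumour proves not to be ccRCC is removed from the analysis. If 17 are enrolled and any are lost in these ways, the test runs on fewer pairs than the power statement assumes.

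A reader cannot tell whether 54%/74% is the planned power or the best case. The remark that the estimate is conservative does not help, because it rests on the size of the pilot correlation and says nothing about lost patients. Section 1.1 also says the results may be used to size later studies, and the number of analysed pairs governs how precise that estimate is.

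**Working it through.** **Inputs from the documents.** Enrolled: 17 (7.2). N in the power statement: 17 (7.3). Alpha 0.05, Spearman test, rho = 0.5 and 0.6, stated power 54% and 74% (7.3). Not given: sidedness, power formula, expected loss rate.

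**Step 1: reproduce the stated figures.** Two-sided Fisher z: power = Φ(atanh(rho) × √(N − 3) − 1.96).

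- rho = 0.5, N = 17: 0.5493 × 3.7417 − 1.96 = 0.095, so power is 53.8%.
- rho = 0.6, N = 17: 0.6931 × 3.7417 − 1.96 = 0.634, so power is 73.7%.

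Both match 7.3. A one-sided test gives 65.9% and 82.9% and does not match, so two-sided is assumed below.

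**Step 2: same formula with fewer analysed pairs.**

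| Pairs analysed | rho = 0.5 | rho = 0.6 |
|---|---|---|
| 17 | 53.8% | 73.7% |
| 16 | 50.8% | 70.5% |
| 15 | 47.7% | 67.0% |
| 13 | 41.2% | 59.2% |

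Losing two patients costs 53.8 − 47.7 = 6.1 points at rho = 0.5 and 73.7 − 67.0 = 6.7 points at rho = 0.6.

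**Step 3: does the choice of method matter?** Five methods, all two-sided at 0.05:

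| Method | N = 17 (rho 0.5 / 0.6) | N = 15 | Drop in points |
|---|---|---|---|
| Fisher z, variance 1/(N − 3) | 53.8 / 73.7 | 47.7 / 67.0 | 6.1 / 6.7 |
| Variance 1.06/(N − 3) | 51.5 / 71.2 | 45.6 / 64.5 | 5.9 / 6.7 |
| Variance (1 + rho²/2)/(N − 3) | 49.1 / 66.6 | 43.4 / 59.9 | 5.7 / 6.7 |
| t-based critical r with bias term | 55.8 / 75.7 | 49.9 / 69.4 | 5.9 / 6.3 |
| Simulation, population Spearman 0.5 / 0.6, no ties | 52.8 / 72.4 | 46.9 / 66.0 | 5.9 / 6.4 |

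The level depends on the method; the cost of two losses hardly does. The fourth method gives 52.9/72.7 at N = 16, close to the stated figures, so reproduction alone does not identify N. It does not need to, since 7.3 states N = 17.

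**Step 4: assumed loss rates.** With independent losses from 17 enrolled, the chance that all 17 are analysed is (1 − d)^17. Average power uses the Step 1 formula over the binomial distribution of N.

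| Assumed loss d | Chance of no loss | Average power (rho 0.5 / 0.6) | Enrolment for 17 evaluable, 17/(1 − d) rounded up |
|---|---|---|---|
| 5% | 42% | 51.2% / 70.9% | 18 |
| 10% | 17% | 48.6% / 67.9% | 19 |
| 20% | 2% | 43.1% / 61.2% | 22 |

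**Step 5: at the pilot correlation.** With rho = .896 and N = 13, the four formulas give 99.6%, 99.4%, 97.2% and 99.7%. Losses on this scale hardly matter if the pilot correlation is true.

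**The case against.** The strongest reply is that nothing in 7.3 is false. It is conditional on N = 17 and correct for 17 pairs. Sections 1.1, 7.2 and 7.3 all use 17, and one reading fits them together: 17 usable ccRCC cases, with 7.2 loosely worded. That reading is possible, but no passage states it, and under it 7.2 still misdescribes accrual.

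The word eligible in 7.2 could also carry weight. Some criteria can be failed on the scan day (glucose in 3.2.4, the pregnancy test in 3.1.8, MRI tolerance in 3.2.1), and section 4.2 excludes anyone who fails eligibility along the way. The 17 might therefore already be net of those failures, which is why I do not count them as separate losses. Other withdrawals under 4.5 and the histology exclusion remain, because eligibility is met on suspicion alone.

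Three further points stand in part. Section 6.1 concerns safety, so it only supports what 7.1 and 4.5 already establish. The methods differ by 55.8 − 49.1 = 6.7 points at N = 17 and rho = 0.5, about as much as losing two patients, and the simulation ignores the ties that a fraction of at most ten cores will produce; any restated power should therefore name its method. And the study calls itself preliminary and openly states low power, which limits the consequence.

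**Conclusion.** The concern holds. If 17 is the number enrolled, 54%/74% is a zero-loss maximum, and each patient withdrawn before the scan or found to have another histology lowers it. The first loss costs about 3 points, and two losses cost 5.7 to 6.7 points across the five methods and both correlations. If 17 means imaged with suspected ccRCC, only the histology exclusion remains as a loss. If it means imaged and confirmed, 7.3 stands and only 7.2 needs rewording. The text does not settle which applies, but a passage needs correcting in each case.

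This rests on a two-sided test, on illustrative loss rates, and on the readable text: the schema graphic in 4.1 is not available, so the absence of a replacement rule is established for the text only. It should be fixed, but its effect is modest, and the endpoint and test are untouched.

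**What to change.** In 7.3, state power by number evaluable, defined as confirmed ccRCC with both FTVOT2 and a ccB fraction available: about 54%/74% at 17, 48%/67% at 15 and 41%/59% at 13 for rho = 0.5/0.6. Name the approximation and the sidedness, and mark the rows as illustrative. Align 1.1 with 7.2 so that both give 17 as the enrolled number. This costs wording in 1.1, 7.2 and 7.3 and a slightly less favourable stated power; it needs no extra patients.

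If 17 evaluable was intended, 7.2 should say so and state that non-evaluable patients are replaced; 7.3 can then stand. Only this alternative adds enrolments: about 18, 19 or 22 in total at an assumed loss of 5%, 10% or 20%.

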7.3 Data Analysis Plans

For the primary endpoint, each subject's FTVOT2 will be correlated with the primary outcome (fraction of core classified as ccB) and correlation estimated using the non-parametric Spearman correlation test.

Regarding the specific hypothesis testing of PET FTVOT2, with $N = 17$, we will have approximately 54% power to detect a correlation of $\rho = 0.5$ (and 74% power to detect $\rho = 0.6$), with a Type I error rate of 0.05 and utilizing the Spearman correlation test. This is considered a conservative estimate. Data from the prior study¹ shows a strong Spearman correlation ($\rho = .896$, $p = .006$) between the fraction of core samples classified as ccB and the PET tumor volume fraction over SUV 2.0 (FTVOT2).

¹ S. A. Brooks et al., "Alternate metabolic programs define regional variation of relevant biological features in renal cell carcinoma progression," *Clinical Cancer Research*, Jan 19, 2016. (PMID: 26787754)

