1.0 BACKGROUND AND RATIONALE

1.1 Study Synopsis

The objective of this study is to evaluate the utility of simultaneous positron emission tomography (PET) and magnetic resonance imaging (MRI) in characterizing the molecular subtypes of clear cell renal cell carcinomas (ccRCC) to potentially inform prognosis and treatment decisions. Previous results on a small number of subjects at UNC demonstrated a relationship between PET-MRI imaging characteristics and tumor subtype composition as determined by transcriptome analysis of surgical core samples in ccRCC. ccRCC has been classified into two molecular subtypes, ccA and ccB, on the basis of expression of a group of 34 genes; the two subtypes have been shown to have clear differences in prognosis. These tumors are notoriously heterogeneous; a single tumor can contain both subtypes, and full tumor molecular characterization is infeasible. Imaging, however, offers a snapshot of the whole tumor. If imaging characteristics prove to be predictive of subtype composition, early prognostic information would be available and different approaches to treatment may be enabled.

In this project, we will image 17 ccRCC subjects on simultaneous PET-MRI and quantify the metabolically-active fraction of the tumor from images. Up to ten core samples will be taken from each tumor post-surgery and classified as ccA or ccB subtype using transcriptome analysis. The imaging-based measures will be correlated with the fraction of tumor cores classified as ccB. We hypothesize that the metabolically-active tumor volume fraction derived from simultaneous PET-MRI imaging is correlated with the fraction of tumor cores classified as ccB subtype from transcriptome analysis.

This study is designed to provide preliminary information on the relationship between imaging metrics and tumor subtype composition in 17 ccRCC subjects. The primary objective is to evaluate the capabilities of MRI/PET in prediction of ccB burden.

Information from this study may be used to estimate effect size for power calculation and sample size considerations for possible future studies in the use of combined PET-MR to be used for prognostic information in ccRCC cases and potentially to enable risk-stratification that is not currently possible.

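### Does section 7.3 need a planned confidence interval for the primary Spearman correlation?

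*Combined protocol and SAP*

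**What the plan says.** Section 7.3 is the whole analysis plan for the primary endpoint. Each subject's FTVOT2 is set against the fraction of cores classified as ccB, with "correlation estimated using the non-parametric Spearman correlation test". The power statement gives about 54% at a correlation of 0.5 and 74% at 0.6 for N = 17, "with a Type I error rate of 0.05 and utilizing the Spearman correlation test". It does not say whether the test is two-sided. No section plans a confidence interval or standard error for the correlation.

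Section 1.1 describes the purpose: "This study is designed to provide preliminary information on the relationship between imaging metrics and tumor subtype composition". It adds: "Information from this study may be used to estimate effect size for power calculation and sample size considerations for possible future studies".

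Three places bear on how many patients will be analysed. Section 7.2 says "The study will enroll 17 eligible patients that are being treated at UNC Hospitals". Criterion 3.1.3 reads "Must have clinically-suspected ccRCC based on prior imaging", so histology is not confirmed at entry. Section 7.1 says "Non-ccRCC histologies will be excluded from further analysis". No replacement rule is given, though section 1.1 speaks of imaging 17 subjects with ccRCC.

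**The concern.** A study whose result may be used to size later studies ought to convey how uncertain its effect size is. At N = 17 that uncertainty is large over the range the plan itself considers. An observed 0.6 would be significant and, taken alone, points to a follow-up study of about 20 patients for 80% power. The limits of its 95% interval correspond to several hundred patients at one end and fewer than ten at the other. A planner shown only the estimate and a p-value could take 0.6 as settled.

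Two things sharpen the worry. The number analysed may fall below 17 if some tumours prove not to be ccRCC and those patients are not replaced. And the stated power appears to come from a formula for the Pearson correlation, while the planned test is Spearman's.

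**Working it through.** **Inputs.** From section 7.3: N = 17, error rate 0.05, correlations 0.5 and 0.6, stated power about 54% and 74%, pilot correlation 0.896. From section 7.1: up to ten cores per tumour. The documents give no rate of non-ccRCC histology, so 15 and 13 analysed patients are assumptions (2 or 4 lost and not replaced).

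**1. The plan's own figure.** Two-sided Fisher z power is Phi(atanh(rho) × sqrt(N - 3) - 1.960).
- rho = 0.5: 0.5493 × 3.7417 - 1.960 = 0.095, power 53.8%.
- rho = 0.6: 0.6931 × 3.7417 - 1.960 = 0.634, power 73.7%.

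Both agree with section 7.3. The one-sided version gives 65.9% and 82.9%, so a two-sided test was evidently meant. Simulation of the two-sided Spearman test, with the population Spearman correlation set to 0.5 and 0.6, gives 53% and 72% for continuous data. With ties as in a ten-core fraction it gives 54% and 73-74%. The stated figures therefore suit the planned endpoint about as well as any replacement would.

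**2. The interval at N = 17.** Bonett-Wright: tanh(atanh(r) ± 1.96 × sqrt((1 + r²/2)/(N - 3))). Plain Fisher z uses 1/(N - 3) as the variance.

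| Observed r | Bonett-Wright 95% CI | Fisher z 95% CI |
|---|---|---|
| 0.5 | -0.006 to 0.802 | 0.025 to 0.79 |
| 0.6 | 0.123 to 0.852 | 0.168 to 0.84 |
| 0.896 | 0.68 to 0.97 | 0.73 to 0.96 |

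Worked line for r = 0.5: sqrt(1.125/14) = 0.2835; × 1.96 = 0.5556; 0.5493 - 0.5556 = -0.0063 and 0.5493 + 0.5556 = 1.1049; tanh gives -0.006 and 0.802.

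In simulation with true correlations of 0.5 and 0.6, the Bonett-Wright interval covers 95.8% to 96.1% of the time, with or without ties. The standard formula is therefore adequate here without special provision.

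**3. With fewer analysed (Bonett-Wright).** N = 15: -0.05 to 0.82 at r = 0.5, and 0.08 to 0.86 at r = 0.6. N = 13: -0.11 to 0.84, and 0.02 to 0.88. Only r and N enter the formula, so a reader who knows how many were analysed sees this loss at once.

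**4. Meaning for a follow-up study.** N for 80% power = 3 + (2.802/atanh(r))², where 2.802 = 1.960 + 0.842.
- r = 0.6: 19.3, so 20.
- Bonett-Wright limits of the 0.6 interval: 513 and 8.
- Fisher z limits: about 277 and 9.

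The range is very wide under either formula, and a later planner can compute it from r and N.

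**5. Where the choice of formula matters.** The Spearman test (t approximation, 15 degrees of freedom) is significant at N = 17 when r exceeds 2.131/sqrt(2.131² + 15) = 0.482. The Fisher z interval excludes zero from r = tanh(1.96/3.7417) = 0.481, practically the same point. The Bonett-Wright interval excludes zero only from r of about 0.505. Test and interval can therefore disagree only between about 0.482 and 0.505.

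**The case for a change.** The best case for amending section 7.3 is that an interval left to the analyst is also left to the analyst's choice of method. At r = 0.5 that choice moves the lower limit from 0.03 to -0.01, across zero. A named method would remove the choice at the cost of one sentence. Significant results also tend to exaggerate: in simulation with a true correlation of 0.5 and N = 17, estimates that reach significance average about 0.63. The pilot result is itself quoted in section 7.3 with only a correlation and a p-value, which suggests the new result may be presented in the same way.

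Some of this stands. No interval method is fixed in advance, and a sentence naming one would do no harm. But the inference rests on the Spearman test, which is named, and the disputed band of observed values is only about 0.02 wide. Section 7.3 plans the estimate whatever the p-value, so nothing in the plan invites selective reporting. An interval around an estimate selected for significance would not undo the exaggeration either. The pilot example also shows that the information is recoverable. From 0.896 and the eight subjects mentioned in section 1.2, Bonett-Wright gives 0.39 to 0.99.

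Whether patients with other histologies are replaced is a separate question about numbers, which an interval does not answer.

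**Conclusion.** No change to the plan follows. Section 7.3 omits a customary reporting detail; it contains no wrong figure and no invalid method. Followed exactly, it produces a valid Spearman correlation and test for the stated objective. The missing interval is a fixed function of the correlation and the number analysed, so an analyst would ordinarily add it and a later planner can derive it.

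The imprecision is real but comes from 17 patients, which the study accepts by calling itself preliminary. Adding an interval to the plan would not narrow it. By Bonett-Wright its width is about 0.81 at an observed 0.5 and 0.73 at 0.6, but about 0.29 at 0.896, so how imprecise the result proves depends on what is observed. The stated power is sound as an approximation for 17 analysed patients, and restating it as 53% and 72% would gain nothing. Writing expected widths for 13 patients into the protocol would add figures that rest on an assumed loss.

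This conclusion assumes that the report will give the correlation and the number analysed, and that the test is two-sided, as the power figures imply.

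### Does the 54%/74% power in section 7.3 overstate what the planned Spearman test can achieve?

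*Combined protocol and SAP*

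**What the plan says.** Section 7.3 plans a Spearman correlation between each subject's FTVOT2 and the fraction of cores classified as ccB. For 17 patients it says "we will have approximately 54% power to detect a correlation of" 0.5, "and 74% power to detect" 0.6, "with a Type I error rate of 0.05 and utilizing the Spearman correlation test". It adds: "This is considered a conservative estimate". The next sentence gives the pilot result, a Spearman correlation of 0.896 between the core fraction and FTVOT2.

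Section 7.2 fixes the number: "The study will enroll 17 eligible patients that are being treated at UNC Hospitals". Section 7.1 describes the outcome: "Up to ten samples will be taken from each tumor, spatially distributed", and the fraction that is clearly ccB goes into the analysis. Section 1.1 puts the aim more broadly: "The primary objective is to evaluate the capabilities of MRI/PET in prediction of ccB burden".

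The plan gives no formula for the power, does not say whether the test is one- or two-sided, and does not say in words which population correlation rho is.

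**The concern.** There are three reasons for suspicion.

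- The two percentages match the textbook Fisher-z power for a Pearson correlation with standard error 1/sqrt(N−3), although the sentence names the Spearman test. A rank correlation usually has a larger standard error, and the common correction (variance 1.06/(N−3)) gives lower power.
- The outcome is not continuous. It is a proportion of at most ten cores, with ties.
- If rho means the association with the ccB burden of the whole tumour, sampling a few cores weakens the correlation that can be observed, and the calculation makes no allowance for this.

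If the power were materially lower than stated, a non-significant result would be read with too much confidence, and calling the estimate conservative would be wrong. Section 1.1 also says the results may feed the planning of later studies.

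**Working it through.** **Inputs.** N = 17 (section 7.2); alpha 0.05, the Spearman test, rho = 0.5 and 0.6, stated power 54% and 74% (section 7.3); up to ten cores per tumour (section 7.1). Sidedness is not stated and is inferred in step 1.

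**1. The plan's own figures.** Power = Φ(atanh(rho) × sqrt(N−3) − 1.96), two-sided 0.05.

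- rho = 0.5: 0.5493 × 3.7417 = 2.055; 2.055 − 1.960 = 0.095; Φ = 53.8%.
- rho = 0.6: 0.6931 × 3.7417 = 2.594; 2.594 − 1.960 = 0.634; Φ = 73.7%.

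These round to 54% and 74%. A one-sided test would give 65.9% and 82.9%, so the calculation was two-sided, with no rank adjustment.

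**2. Does the formula's origin make the figures too high?** Not by itself, because all these formulas are approximations at N = 17.

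- The unadjusted formula understates the power of the Pearson test. Simulated, that test has 56.3% and 76.4% when rho is the Pearson correlation, and adding the formula's bias term gives 56.1% and 75.9%. The missing bias term and the missing rank adjustment pull in opposite directions.
- Variance 1.06/(N−3) gives 51.5% and 71.2%.
- Variance (1 + rho²/2)/(N−3), applied throughout, gives 49.1% and 66.6%. But that variance reduces to 1/(N−3) when rho = 0, so the rejection limit should not be inflated. Inflating only under the alternative gives Φ(0.095/1.061) = 53.6% and Φ(0.634/1.086) = 72.0%.

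The formulas disagree by several points, so the planned test itself has to be simulated.

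**3. Which correlation is rho?** Section 2.1 names the fraction of ccB-positive cores. Section 7.1 sets the primary endpoint as FTVOT2 against the fraction of cores classified as ccB. Section 7.3 repeats that pair for the test, and its pilot value of 0.896 is a Spearman correlation of the same pair. The natural reading is the population Spearman correlation between FTVOT2 and the observed core fraction.

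**4. The planned test on that scale.** Two-sided Spearman test with the t approximation, N = 17, 60,000 replicates per cell (Monte Carlo standard error sqrt(0.53 × 0.47/60,000) = 0.2 points). Core counts are binomial around a Beta-distributed tumour fraction, with the latent correlation tuned so that the Spearman correlation with the observed, tied fraction is 0.5 or 0.6. The Beta shapes and independent cores are assumptions; four shapes show the range.

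| Tumour ccB fraction | Cores | Power, rho 0.5 | Power, rho 0.6 |
|---|---|---|---|
| Beta(1, 1) | 10 | 53.0% | 72.7% |
| Beta(1, 1) | 5 | 52.9% | 73.3% |
| Beta(0.5, 0.5) | 10 | 52.8% | 72.8% |
| Beta(0.5, 0.5) | 5 | 53.1% | 73.3% |
| Beta(0.3, 0.7) | 10 | 53.2% | 73.4% |
| Beta(0.3, 0.7) | 5 | 53.8% | 73.8% |
| Beta(0.2, 0.8) | 10 | 53.9% | 73.4% |
| Beta(0.2, 0.8) | 5 | 53.9% | 74.2% |

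The largest shortfalls are 54 − 52.8 = 1.2 points and 74 − 72.7 = 1.3 points; in one cell power is 0.2 points above the stated figure. Neither the ties nor the drop from ten to five cores lowers power materially when rho is the correlation under test.

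**5. Where larger losses come from.** They appear when rho is defined differently (two-sided Spearman test, N = 17):

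| Meaning of rho | Power, rho 0.5 | Power, rho 0.6 |
|---|---|---|
| Spearman, both variables continuous | 52.7% | 72.2% |
| Pearson, bivariate normal | 49.5% | 68.9% |
| Spearman with the true tumour fraction, 10 cores | 41.1–47.5% | 57.9–66.3% |
| Spearman with the true tumour fraction, 5 cores | 36.8–43.7% | 51.7–61.1% |

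The last two rows reflect attenuation: a correlation of 0.5 with the true fraction is a smaller correlation with the core fraction, and the smaller one is tested. They do not show a fault in the power for the correlation that section 7.3 names.

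**The case for a change.** The best opposing case is that the plan never says in words what rho is. Section 1.1 speaks of predicting ccB burden, and section 1.2 of burden across the entire tumour. For that quantity core sampling does cost power: with ten cores, 54 − 47.5 = 6.5 to 54 − 41.1 = 12.9 points at 0.5, and 74 − 66.3 = 7.7 to 74 − 57.9 = 16.1 points at 0.6, and more with fewer cores. The arithmetic is sound given its assumptions. But section 1.1 itself states the hypothesis as a correlation with the fraction of cores classified as ccB, and section 7.3 tests and calibrates on that fraction. A general statement of aim does not redefine the rho of the power sentence. The size of these losses also rests on Beta distributions and independent cores that the documents do not supply.

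A second point is that the plan does not say how the Spearman p-value is obtained. The t approximation used above has a simulated size of 5.2%. With the exact critical value for untied data (0.488 instead of 0.482), the continuous-variable figures fall to 51.8% and 71.4%, which is 2.2 and 2.6 points below the stated ones. The outcome here will be tied, so that untied table does not strictly apply. Even at this size the difference is small against a figure given as approximate.

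Third, the calculation has no conservative element of its own. That is true, but the sentence stands directly before the pilot's 0.896 and reads naturally as a remark on assuming 0.5 to 0.6 instead. That choice is cautious relative to the pilot.

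What stands is that the formula, the sidedness and the scale of rho are not named.

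**Conclusion.** The concern does not hold. The stated 54% and 74% do come from an unadjusted Fisher-z formula, but for the Spearman correlation between the two variables the plan analyses they are right to about 1 point. This rests on 17 analysable pairs, a two-sided test at 0.05 with the t approximation, and rho read as the Spearman correlation with the observed core fraction. It is stable over four assumed spreads of the ccB fraction and over five or ten cores.

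Substituting the 1.06-variance values (51.5% and 71.2%) would not improve the text: on this scale and with the t approximation they lie further from the simulated power than the present figures do.

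Nothing in the study turns on the difference. The sample size is fixed at 17, no decision rule uses the power, and section 1.1 presents the study as preliminary. The plan openly reports low power, and a null result would be read the same way at 53% as at 54%. Later studies would draw on the estimated effect size, which section 1.1 names as the output for planning, and not on this power figure. Naming the method and the scale of rho would be tidier, but would change no number or conclusion.
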